Subjects come to a pre-procedure room on the day of the procedure. The investigator will again go over the risk and benefit of procedure and indication of the procedure. Once the consent form is signed, a large bore IV cannula is placed and the subject will be taken to the DHC procedure room. Once all the team members required to perform the procedure are in the room we will do a time-out to make sure current patient and procedure are performed. A time-out is done by asking the subject to tell his full name with date of birth and describe in his own words what procedure is planned for subject today. If all the things match the investigator will go ahead and start the sedation.

All EUS-FNB was performed in the standard manner using linear echoendoscopes. All EUS-FNB procedures were performed by 1 of 2 highly experienced endosonographers ([name] or [name]).

The needle to be used (SharkCore vs Acquire) will be decided based on randomization software. The needle was then used to puncture the target lesion in standard fashion. Aspirated cellular materials will be expressed into the slide by advancing the stylet. The remainder will be expressed onto filter paper and submitted for cell block preparation. Your medical information including diagnosis, date of diagnosis, date of admission, blood test results, and medications received will be reviewed for analysis.

VII.E.7 Will you attempt to recontact subjects who are lost to follow-up?

No - followup is not required in this study

VII.E.9 Will subjects be provided any compensation for participating in this study?

No

VIII. Risks

VIII.1 What are the risks to subjects including

- emotional or psychological
- financial
- legal or social
- physical?

loss of confidentiality is the risk of study.

- VIII.2 What have you done to minimize the risks?
 - If applicable to this study ALSO include:
 - How you (members of your research team at Iowa) will monitor the safety of individual subjects.
 - Include a description of the availability of medical or psychological resources that subjects might require as a
 consequence of participating in this research and how referral will occur if necessary (e.g. availability of
 emergency medical care, psychological counseling, etc.)

Risk of patients confidentiality is minimized by identification of data and sample via numbers only, with access to data limited to PI and Co-investigator only.

VIII.3 Does this study have a plan to have an individual or committee review combined data from all subjects on a periodic basis (such as summary or aggregate safety and/or efficacy data)?

IX. Benefits

IX.1 What are the direct benefits to the subject (do not include compensation or hypothesized results)? There is no direct benefit to the patients.

IX.2 What are the potential benefits to society in terms of knowledge to be gained as a result of this project?

We hope to identify a better needle that can be used in the future as this will help in better overall safety profile and higher diagnostic accuracy leading to less repeat procedure and delays in appropriate therapy.

X. Privacy & Confidentiality

X.1 What are you doing to protect the privacy interests of the subjects?

We will only collect the subject data required for the study and no more. Informed consents are performed in private rooms.

X.2 Are you collecting the Social Security Number of any subjects for any purpose?

No

X.4 How will information/data be collected and stored for this study (check all that apply):

- Electronic records (computer files, electronic databases, etc.) Electronic records (computer files, electronic databases, etc.) Networked computers at UIHC will be used to collect data from EPIC, Data will be saved in a password protected spreadsheets and stored in a password protected computer, Only PI and research team will have access.
 - o Name [name]
 - o Title Director, Information Security
 - o University Job Classification Faculty/Staff
- X.5 Do the confidentiality protections indicated above allow only members of the research team to access the data/specimens?
 Yes
- X.7 Does your study meet the NIH criteria for a Certificate of Confidentiality or will you be applying for Certificate of Confidentiality?

No

XI. Data Analysis

XI.1 Describe the analysis methods you will use, including, if applicable, the variables you will analyze

we will follow general good statistical practices, including examination of numerical and graphical summaries, an interpretation that reflects estimates, and confidence intervals rather than just p values.and checking for all models assumptio,s. We will perform a univariate analysis, controlling for confounders, as appropriate. All analysis will be performed using StataCorp.2011. Stata Statistical Software: Release 12.College Station, TX: StataCorp LP. The diagnostic accuracy will be calculated considering malignant diagnoses as a true positive. For benign diagnoses, we used

clinical impression and imaging characteristics and a clinical course that was either consistent with (in diagnostic cases) or inconsistent with (in non-diagnostic cases) the study diagnosis.

XI.2 Provide the rationale or power analysis to support the number of subjects proposed to complete this study.

The Diagnostic accuracy of the SharkCore needle is around 80%. Considering a non-inferiority margin of 10% we will need 75 patients in each group.

XII. Future Research

XII.1 Do you wish to keep any information about subjects involved with this research project so that members of the current research team may contact them in the future for your own research projects?

No

XII.2 Do you wish to keep any information about subjects involved with this research project so that other researchers may contact them for future research?

No

XII.4 Does this project involve storing any data, tissues or specimens for future research?

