Since both SharkCore and Acquire needle are FDA approved for EUS guided biopsy and already in use at UIHC these are present in Omnicells which can only be opened with a password. Every time a needle is used the barcode specific for that needle is scanned into EPIC.

VII.B.24 Is the device FDA-approved for the way it will be used in this study?
Yes

VII.C. Project Description (C)

VII.C.1 Does this project involve any research on genes or genetic testing/research?
No

VII.D. Project Description (D)

- VII.D.1 Check all materials/methods that will be used in recruiting subjects (you will need to attach copies of all materials at the end of the application):
 - Use of any information available to the researchers or their colleagues because this person is a patient OR use of any information considered to be Protected Health Information (PHI) OR review of patient/clinic records GI inpatient team/Clinic providers will consult the investigator and study investigator will follow-up with the patient. We also get referrals from outside providers for EUS to help in the diagnosis of malignancy for which EUS biopsy is paramount.
 - Referral from colleague Patients are referred to GI clinic for evaluation and to take Biopsy of mass seen on imaging studies. We
 will review the images and make sure that the patient meets the criterion for endoscopic ultrasound and Biopsy before recruiting
 them into study population.

VII.D.2 List the individual data elements you will need to access/use from the patient or clinic records to identify potential subjects for recruitment

age,sex, reason for hospitalization, diagnosis, date of diagnosis, medication history, travel history (if available), past medical history, imaging study (including but not limited to CT abdomen/pelvis/chest with and without contrast; MRI abdomen/pelvis and Chest, PET scan whole body), lab tests- CBC,BMP, INR, LFT,CEA, CA19-9, AFP, Pathology results.

- VII.D.3 Describe why you could not practicably recruit subjects without access to and use of the information described above we would not know who to approach without assessing PHI and it will be impractical to do an endoscopic ultrasound on all patients coming to the digestive health clinic.
- VII.D.4 Describe why you could not practicably obtain authorization from potential subjects to review their patient or clinic records for recruitment purposes.

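### Benign results have no dated reference that is independent of the study biopsy, so a false-benign result can be confirmed by the impression it created

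*Combined protocol and SAP*

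**What the plan says.** The reference standard is described only in XI.1. For malignancy: "The diagnostic accuracy will be calculated considering malignant diagnoses as a true positive". Benign results are judged by "clinical impression and imaging characteristics and a clinical course that was either consistent with (in diagnostic cases"), meaning a course that fits the study diagnosis; where the sample was non-diagnostic, the course is one that does not fit it. So there are three components: impression, imaging and course. None has a date, a minimum duration or a cut-off, and nothing says whether the person judging them may rely on the biopsy report.

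VII.E.7, on recontacting subjects, answers "No - followup is not required in this study". VII.E.6 describes the record review: "Your medical information including diagnosis, date of diagnosis, date of admission, blood test results, and medications received will be reviewed for analysis". X.4 gives the source: "Networked computers at UIHC will be used to collect data from EPIC". Imaging studies and pathology appear in VII.D.2 as items used to find candidates, in a list that ends "lab tests- CBC,BMP, INR, LFT,CEA, CA19-9, AFP, Pathology results". VII.D.1 adds a look at the images before enrolment: "We will review the images and make sure that the patient meets the criterion for endoscopic ultrasound and Biopsy before recruiting". VII.B.11 states that no separate written protocol exists, so no other document fills the gap.

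**The concern.** A reference standard has to be able to disagree with the test it judges. In XI.1 the benign reference is judged by its agreement with the study diagnosis, and nothing stops that reference from being built on the study sample. Once a benign report is in the chart, the charted impression may simply repeat it. A missed malignancy would then be scored as a correct benign result.

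Diagnostic accuracy is the first item in the non-inferiority question (I.5) and the basis of the sample size (XI.2). Benign results should be expected, because VI.13 admits autoimmune pancreatitis, granulomatous disease and indeterminate hepatitis. If wrong benign results are scored correct in both arms, both accuracies rise. The needle with more misses gains more, so the difference shrinks. In a non-inferiority comparison that weakens the protection against accepting a worse needle.

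**Working it through.** **Text check.** The three components of the benign reference, set against what the plan secures:

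| Component in XI.1 | Fixed before biopsy, or independent of it? | Named in VII.E.6? |
|---|---|---|
| Clinical impression | Not stated | No |
| Imaging characteristics | Not stated; images are reviewed before recruitment (VII.D.1) | No (listed in VII.D.2 for recruitment) |
| Clinical course | No window; follow-up not required (VII.E.7) | No |

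VII.E.6 does name the diagnosis and its date. If these are read after the procedure, they may be the biopsy diagnosis; the plan does not say.

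**The plan's figures.** The plan gives no figure for reference error, so there is none to reproduce on this point. The inputs taken from XI.2 are 75 per group, 80% SharkCore accuracy and a 10-point margin. The 75 is used as stated. With equal 80% accuracy, one-sided 0.025 and 80% power (all three assumed), n = (1.960 + 0.842)² × (2 × 0.80 × 0.20) / 0.10² gives 252 per group. The plan's 75 therefore rests on inputs it does not state. That is a separate matter and does not affect what follows.

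**Illustration 1: gap hidden through benign results.** Assumptions: b = 15 to 30 benign results per arm, false shares of 10% and 30%, and a share c of false-benign results scored correct because the reference copies the biopsy.

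- True gap from these cases = (0.30 − 0.10) × b/75.
- b = 15: 0.20 × 15/75 = 0.04, or 4 points.
- b = 30: 0.20 × 30/75 = 0.08, or 8 points.
- Hidden part = c × gap. With c = 1 all 4 to 8 points are hidden; with c = 0.5, 2 to 4 points.

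**Illustration 2: effect on the conclusion.** Assumptions: true accuracy 80% versus 70%, exactly at the margin; 75 per arm; one-sided 0.025; a share f of all wrong results scored correct. Observed accuracy is p + (1 − p)f. The chance of declaring non-inferiority is Φ[(0.10 − observed difference)/SE − 1.96], with SE = √[p₁(1 − p₁)/75 + p₂(1 − p₂)/75] at the observed accuracies.

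| f | Observed accuracies | Difference (points) | Chance of declaring non-inferiority |
|---|---|---|---|
| 0 | 80% vs 70% | 10 | 2.5% |
| 0.25 | 85% vs 77.5% | 7.5 | 5.9% |
| 0.5 | 90% vs 85% | 5 | 15.1% |
| 0.75 | 95% vs 92.5% | 2.5 | 47.6% |

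For f = 0.5, SE = √[(0.0900 + 0.1275)/75] = 0.0539, and 0.05/0.0539 − 1.96 = −1.03, which gives 15.1%. Neither c nor f is in the documents. The tables show direction and scale, not an estimate.

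**The case against.** The other side has several good points.

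- **The record review is not confined to the charted diagnosis.** A reader might infer that it is. VII.E.6 also covers the admission date, blood results and medications, and the list is open. XI.1 itself says imaging will be used, so not naming it in VII.E.6 does not show that it will be left out. This stands. What remains is that the items XI.1 depends on are unnamed and undated, while X.1 promises to collect only the data the study requires.
- **Clinical course is part of the reference.** It is the component least dependent on the biopsy report, and XI.1 allows for a course that contradicts the study diagnosis in non-diagnostic cases. The reference is therefore not defined as a copy of the biopsy. This stands, but with no window and no required follow-up the course is not secured.
- **A pre-procedure impression may exist.** A reader might infer that none is recorded. The plan is silent. Images are reviewed before recruitment, and VII.D.29 has most patients seen in clinic first.
- **The point overlaps with follow-up.** Later imaging and events would supply much of the missing independence, so this is not a wholly separate defect. A longer record still would not say which evidence may count.
- **The illustration is constructed.** Complete copying is a ceiling, and the counts and false shares are assumed. Equal benign counts with unequal false shares also imply different numbers of truly benign patients by arm. Correcting that enlarges the gap. For example, 13.5 truly benign patients in each arm, all called benign, give 13.5/0.9 − 13.5 = 1.5 and 13.5/0.7 − 13.5 = 5.8 misses, a gap of 4.3/75 = 5.7 points instead of 4. The direction is unchanged.
- **Malignant results are more directly self-referential.** XI.1 counts them as true positives and names no other check. That is true; it widens the question and does not answer it for benign results.

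**Conclusion.** The concern holds in this form: the plan does not keep the benign reference independent of the study biopsy, and it secures neither the timing nor the collection of the evidence that could disagree with it. The likely bias is towards a smaller difference, and so towards non-inferiority when Acquire is truly worse.

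The size is unknown. The 4 to 8 points are what complete copying would hide under the assumed benign counts and false shares. A reader might conclude that 40% to 80% of the 10-point margin is lost. The documents do not support that as a finding: it is the same ceiling divided by the margin, and partial copying hides proportionally less. Nor do they show that the biopsy will be its own reference, only that nothing in the plan prevents it.

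**What to change.** In XI.1, state that a benign result counts as confirmed only by evidence not derived from the study sample: surgery, other sampling already done in care, or later imaging or clinical events in the existing EPIC record. Add these items, with their dates, to VII.E.6.

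Classify benign cases without such evidence as unconfirmed. Report accuracy by arm and the between-needle difference with these cases counted correct and then counted incorrect. Using the same rule in both arms moves the difference only by the difference in unconfirmed shares. An outer bound on the difference therefore also needs the opposite assignment, with unconfirmed cases incorrect for Acquire and correct for SharkCore.

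A dated provisional diagnosis from the existing pre-recruitment image review may be kept as supporting information. It should not by itself overrule the biopsy, because these lesions are sent for histology, some after a non-diagnostic FNA.

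The cost is wording in two sections, a few dated fields from a record already in use, and no added visits. The real downside is width. With no required follow-up, many benign cases may be unconfirmed. If all of the assumed 15 to 30 per arm were, each arm's accuracy would span 15/75 = 20 to 30/75 = 40 points, against a 10-point margin. That width would show how much of the conclusion rests on unverified results.

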I.2 Project Title:

Randomized controlled trial comparing SharkCore FNB needles with Acquire FNB needles regarding specimen quality and Diagnostic accuracy.

- I.3 Short Title (optional):
- I.4 Provide a short summary of the purpose and procedures of the study proposed in this IRB application.
 - DO NOT include information on studies not proposed in this application.
 - Use LAY terminology only. This must be easily understandable by IRB community members and nonscientists.
 - DO NOT cut and paste technical abstracts from funding applications that may not be understood by a general
 audience.

Endoscopic ultrasound-guided fine needle aspiration (EUS-FNA) has been established as an effective technique for sampling tissue inside and around the gastrointestinal tract, including the pancreas, liver, lymph nodes, and adrenal glands. EUS-FNA is convenient, minimally invasive, and safe procedure with an estimated sensitivity of 75%-92% and a specificity of 82%-100%.

Diagnosis of various pathologies in the GI tract including solid pancreatic masses, mediastinal or gastric lymph nodes, gastrointestinal submucosal lesions, and peri-rectal lesions require adequate tissue architecture and immunohistochemical analysis. This is difficult to obtain and is frequently insufficient with EUS-FNA cytology alone. The core tissue is required to improve the diagnostic yield and obtain histologic diagnosis along with immunostaining to establish specimen adequacy. In past 1 year two new needle EUS needle (Shark Core) and Acquire EUS needles has been introduced to improve diagnostic accuracy, tissue yield, and potentially obtain a core tissue sample. So far, no prospective studies have compared these two needles to see which one is better for overall diagnostic accuracy. Our goal is to perform a prospective analysis to compare the diagnostic yield and safety profile of these 2 new EUS needle.

I.5 Specify your research question(s), study aims or hypotheses (do not indicate "see protocol")

Is the new Acquire FNB needle (Boston Scientific, Natick, MA) non-inferior in diagnostic accuracy, histologic yield of the sample obtained, number of needle passes required to obtain the tissue sample, ability to get tissue core to allow IHC staining and molecular diagnostics and side effect profile, when compared to SharkCore needle (Medtronic, Dublin, Ireland)?

I.6 Background and significance and/or Preliminary studies related to this project.
(do not indicate "see protocol")

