VII.D.37 Does the study include any form of deception (e.g., providing participants with false information, misleading information, or withholding information about certain study procedures)?

Examples:

- Procedure includes a cover story that provides a plausible but inaccurate account of the purposes of the research.
- Participants will be provided with false information regarding the particular behaviors of interest in the research.
- Procedures include a confederate pretending to be another participant in the study.
- Participants will be told that the research includes completion of a particular task, when in fact, that task will not be administered.
- Study is designed to introduce a new procedure (or task) that participants are not initially told about.
- If yes, a waiver of informed consent must be requested under question IV.3.

No

VII.E. Project Description (E)

VII.E.1 Will subjects be randomized?

Yes

VII.E.1.a Will any subjects be blinded to which study arm they have been assigned?
No

VII.E.2 Describe randomization scheme/assignment including ratio such as 1:1, 2:1 etc.

we will use 1:1 randomization.

VII.E.3 Will any questionnaires, surveys, or written assessments be used to obtain data directly from subjects in this study?

VII.E.5 Does this project involve creating any audiotapes, videotapes, or photographs?

Νo

VII.E.6 Provide a detailed description in sequential order of the study procedures following the consent process - DO NOT cut and paste from the Consent Document.

Describe study populations separately if they will be participating in different procedures - include CONTROL population if applicable.

DESCRIBE:

- What subjects will be asked to do/what happens in the study (in sequential order)
- The time period over which procedures will occur
- The time commitment for the subject for individual visits/procedures
- Long-term followup and how it occurs

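### No masking of outcome assessment is specified for benign and non-diagnostic cases, and the record used to judge them also holds the needle barcode

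*Combined protocol and SAP*

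**What the plan says.** Section I.5 asks whether Acquire is "non-inferior in diagnostic accuracy" to SharkCore, among several other outcomes. No outcome is labelled primary, but accuracy is named first and is the only one sized. XI.2 states "The Diagnostic accuracy of the SharkCore needle is around 80" per cent and "Considering a non-inferiority margin of 10" per cent, and arrives at 75 patients per group.

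XI.1 treats malignant diagnoses as true positives. For benign diagnoses it relies on "clinical impression and imaging characteristics" and on whether the clinical course fitted the study diagnosis (diagnostic cases) or did not (non-diagnostic cases). It names no assessor.

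Four other places bear on masking:

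- VII.E.1.a asks "Will any subjects be blinded to which study arm they have been assigned"; the answer is no.
- VII.B.23 says "Every time a needle is used the barcode specific for that needle is scanned into EPIC".
- X.4 says "Networked computers at UIHC will be used to collect data from EPIC", with access for the PI and research team.
- VIII.2 describes "identification of data and sample via numbers only" as a protection of confidentiality, with access for the PI and Co-investigator only.

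The visible text says nothing about masking the pathologist, the person who classifies cases, or the analyst.

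**The concern.** For a case without a malignant result, correct or incorrect is a judgement. It is made from the same record system that identifies the needle, and nothing in the described flow removes that field first. If the classifier knows the needle, borderline cases can be read more generously in one arm, and the accuracy difference is biased directly. Analysis cannot remove such bias afterwards.

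Differing expectations are plausible. VII.B.19 reports more than one year of local use of SharkCore and more than two months of Acquire. With small arms and a 10-point margin, a handful of calls could matter. The operators cannot be masked to the needle, but the person who classifies can be.

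**Working it through.** **Inputs.** SharkCore accuracy 0.80, margin 0.10 and 75 per arm (XI.2); 1:1 allocation (VII.E.2). Assumed because not stated: the margin is absolute; Acquire accuracy is 0.80 unless varied; one-sided alpha is 0.025 (95% CI), with 0.05 (90% CI) as the alternative.

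**The plan's own figure.** n per arm = (z_α + z_β)² × [p₁(1−p₁) + p₀(1−p₀)] / margin². With 80% in both arms and 80% power:

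- one-sided 0.025: (1.960 + 0.842)² × 0.32 / 0.01 = 252
- one-sided 0.05: (1.645 + 0.842)² × 0.32 / 0.01 = 198

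The stated 75 is not reproduced. At 75 per arm, power is about 33% or 45%. That is a separate problem, but it explains part of the fragility below.

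**Tipping point.** One call moves an arm by 1/75 = 1.33 points. Hold SharkCore at 60/75 and add Acquire successes one at a time. The Wald lower limit is d − z × √[p₁(1−p₁)/75 + p₀(1−p₀)/75], where d = p₁ − p₀.

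- 60/75, 95%: 0 − 1.960 × 0.0653 = −12.8 points
- 62/75, 95%: 0.0267 − 1.960 × 0.0636 = −9.8 points

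The Newcombe limit combines the Wilson limits of each arm. The score limit (Farrington–Manning) uses rates constrained to the tested difference. Lower limits in points; a pass is above −10:

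| Acquire | Wald 95% | Newcombe 95% | Score 95% | Wald 90% |
|---|---|---|---|---|
| 60/75 | −12.8 | −12.8 | −13.0 | −10.7 |
| 61/75 | −11.3 | −11.4 | −11.5 | −9.3 (pass) |
| 62/75 | −9.8 (pass) | −9.9 (pass) | −10.01 | −7.8 (pass) |
| 63/75 | −8.3 (pass) | −8.4 (pass) | −8.5 (pass) | −6.3 (pass) |

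From equality, the result changes with one call (90% CI), two (Wald or Newcombe 95%) or three (score 95%). The count also depends on the SharkCore result. Under Wald 95% it is three calls at 58/75 and one at 64/75.

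**Equal leniency.** Two extra calls in each arm give 62/75 versus 62/75. The lower limit is −1.960 × √(2 × 0.8267 × 0.1733 / 75) = −1.960 × 0.0618 = −12.1 points, which still fails.

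**Error rates.** Exact binomial enumeration at 75 per arm, Wald 95%, SharkCore truly at 0.80. An average of k lenient Acquire calls is modelled as a scored rate of 0.70 + k/75:

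| Average lenient calls | Scored Acquire rate | Chance of declaring non-inferiority |
|---|---|---|
| 0 | 0.700 | 2.6% |
| 2 | 0.727 | 5.9% |
| 3 | 0.740 | 8.6% |

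Adding exactly two successes instead gives 6.3%. With a 90% CI, exactly two raise the rate from 5.0% to 10.9%. If both needles are truly at 80%, exactly two raise the pass rate from 33.9% to 51.8% (95% CI), so they change the result in about 18% of trials.

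**The case against.** A reader might infer that the assessment is unmasked and that the classifier sees the needle. The documents do not establish this. They do not say who classifies. VII.E.6 lists the record items to be reviewed (diagnosis, dates, blood tests, medications), and needle identity is not among them. VII.E.1.a concerns subjects only, so it cannot be read as saying that assessors know the arm. Some pages were also removed before review. All of this stands: the supportable statement is that no masking is specified and the data source holds the allocation.

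A reader might also infer that two lenient calls decide the trial. That holds only with a Wald or Newcombe 95% limit, results near 60/75 in both arms, and leniency confined to Acquire. The size and direction of leniency are assumptions. The documents show no stake in Acquire: no study device comes from a sponsor (V.25.c), there is no external budget (V.25.f), and both needles are in routine use (VII.B.19). This limits the claim about size but does not remove the route by which bias could enter.

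Coding by number (VIII.2) might be read as masking. It is offered as a confidentiality measure and does not take the needle field out of the source record.

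Finally, masking does not define the judgement. XI.1 gives no criteria or observation window, and VII.E.7 says follow-up is not required. That is a fair criticism of the plan, but it is a separate gap.

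**Conclusion.** The concern holds in this form: the plan specifies no masked classification for benign and non-diagnostic cases, and its described data flow leaves a judgement-based main outcome open to arm-specific bias. It is worth correcting, with medium confidence, because actual exposure of the classifier is possible but not documented.

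The size is conditional: one to three Acquire-only calls from equality at SharkCore 60/75, depending on the interval, and no change if leniency is equal. At a true 70% versus 80%, an average of two or three such calls raises a 2.6% error rate to about 5.9% or 8.6% (Wald 95%). These figures rest on an absolute 10-point margin, 75 evaluable patients per arm and the assumed alpha. Part of the fragility belongs to the sample size and should not be charged to this point.

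**What to change.** State in VII.E.6 and XI.1 that:

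1. The needle brand is left off pathology requests and specimen labels. Normal clinical identifiers stay, because these are standard-of-care specimens and the result is the patient's own diagnosis.
2. An existing research team member who was not in the procedure room classifies each case as accurate or not, from a numbered extract with the needle barcode and the procedure-note needle field removed.
3. The allocation is merged only after all classifications are locked.

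Reconcile VIII.2 (access for the PI and Co-investigator only) with X.4 (PI and research team), so that this person has access. VII.D.12 lists a team well beyond the two endosonographers in VII.E.6, so a suitable member probably exists; the sponsor should confirm it.

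The cost is a few sentences and one extra extraction step, with no added patients, visits or procedures. The downside is that the proceduralist cannot classify outcomes.

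### 75 per group does not follow from 80% accuracy and a 10-point margin: with both needles at 80% power is about 33–46%, and 60/75 correct in each arm would miss the margin

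*Combined protocol and SAP*

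**What the plan says.** Section I.5 poses a non-inferiority question, with diagnostic accuracy listed first: "Is the new Acquire FNB needle (Boston Scientific, Natick, MA) non-inferior in diagnostic accuracy", SharkCore being the comparator. Section VII.E.2 sets the allocation: "we will use 1:1 randomization".

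The sample-size rationale in XI.2 is two sentences long. The first gives the planning value, "The Diagnostic accuracy of the SharkCore needle is around 80" per cent. The second gives the result: "Considering a non-inferiority margin of 10% we will need 75 patients in each group".

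XI.2 states no alpha, sidedness, target power, expected Acquire accuracy, formula or allowance for non-evaluable patients. Section XI.1 says interpretation will reflect estimates and "confidence intervals rather than just p values", but gives no confidence level.

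**The concern.** A non-inferiority comparison of two proportions near 80% with a 10-point margin normally needs some hundreds of patients per group. Seventy-five is well below that, and XI.2 gives nothing from which a reader could rebuild it.

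This is the only sample-size justification for the trial's non-inferiority question. If the number is too small for the stated margin, two equally accurate needles would more often than not produce a trial that fails to show non-inferiority. That failure could then be read as evidence against Acquire when it reflects only the width of the interval.

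**Working it through.** **Inputs from the document**
- SharkCore accuracy: 80% (XI.2).
- Margin: 10%, read as 10 percentage points (XI.2).
- Stated size: 75 per group (XI.2).
- Allocation: 1:1 (VII.E.2).
- Attrition: none applied. XI.2 has no allowance, and VII.E.7 says "No - followup is not required in this study".

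**Assumptions, because the document is silent**
- Acquire accuracy equal to SharkCore at 80%; other values are tried below.
- One-sided alpha 2.5% or 5%; power 80% or 90%.

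**1. Attempt to reproduce 75**

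n per group = (z_alpha + z_beta)² × [0.8×0.2 + 0.8×0.2] / 0.10² = (z_alpha + z_beta)² × 32

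| One-sided alpha | Power | Calculation | n per group |
|---|---|---|---|
| 2.5% | 80% | 7.849 × 32 = 251.2 | 252 |
| 2.5% | 90% | 10.507 × 32 = 336.2 | 337 |
| 5% | 80% | 6.183 × 32 = 197.8 | 198 |
| 5% | 90% | 8.564 × 32 = 274.0 | 275 |
| 10% | 80% | 4.508 × 32 = 144.3 | 145 |
| 10% | 60% | 2.356 × 32 = 75.4 | 76 |

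Under equal accuracy, only about one-sided 10% with 60% power comes near 75, and that is not a conventional pair. Reading the margin as relative (10% of 80%, or 8 points) raises the requirement to 393 per group (one-sided 2.5%, 80% power).

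**2. Power at 75 per group, both needles at 80%**

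SE = √(0.32/75) = 0.0653, so margin/SE = 0.10/0.0653 = 1.531.
- One-sided 2.5%: Φ(1.531 − 1.960) = Φ(−0.429) = 33.4%.
- One-sided 5%: Φ(1.531 − 1.645) = Φ(−0.114) = 45.5%.

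Exact binomial enumeration agrees:

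| Test | One-sided 2.5% | One-sided 5% |
|---|---|---|
| Wald | 33.9% | 45.8% |
| Newcombe | 33.8% | 45.8% |
| Farrington–Manning | 32.5% | 45.1% |

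**3. Result if both arms are observed at 60/75**

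The difference is 0.
- Two-sided 95%: lower limit = −1.96 × 0.0653 = −12.8 points.
- Two-sided 90%: lower limit = −1.645 × 0.0653 = −10.7 points.

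Both lie beyond −10. Newcombe limits are −12.8 and −10.8. The Farrington–Manning z is 1.52, below 1.645 and 1.960.

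With SharkCore at 60/75, Acquire would need 62/75 to pass at 95% (lower limit −9.8; 61/75 gives −11.3). At 90% it would need 61/75 (lower limit −9.3).

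**4. Margin that 75 per group supports at 80% power**
- One-sided 2.5%: (1.960 + 0.842) × 0.0653 = 18.3 points.
- One-sided 5%: (1.645 + 0.842) × 0.0653 = 16.2 points.

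**5. What would yield about 75 at 80% power**
- *Acquire better, one-sided 2.5%:* at 87%, 7.849 × (0.16 + 0.1131)/0.17² = 74.2, so 75.
- *Acquire better, one-sided 5%:* at 85%, 79. At 86%, 6.183 × (0.16 + 0.1204)/0.16² = 67.7, so 68. The value lies between 85% and 86%.
- *Both needles more accurate:* 95% gives 75 at one-sided 2.5%. At one-sided 5%, 93% gives 81 and 94% gives 70.

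**The case against.** The strongest reply is that 75 may not be a miscalculation. The formula returns exactly 75 for Acquire at 87%, SharkCore at 80%, one-sided 2.5% and 80% power, so the fault could be an undisclosed assumption. The power figures also depend on equal true accuracy: at 75 per group, power (one-sided 2.5% / 5%) is 68% / 78% if Acquire is truly 85% accurate and 93% / 97% if it is 90%. The answer to I.6 (background and preliminary studies) is not in the text available for review, so an expected Acquire accuracy could have been given there.

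This stands as a possible explanation of where 75 came from. It does not rescue XI.2, which derives 75 from the SharkCore accuracy and the margin alone. An assumed advantage of 5 to 7 points would carry the whole design and belongs beside the number it produces. Neither I.5 nor XI.2 mentions one.

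A second point also stands as a limit on scope. Equal observed accuracy fails the margin at the planned 80%, but not at every level. It would pass if both observed rates exceeded about 89% (95% interval) or 83% (90% interval).

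Third, the emphasis in XI.1 on estimates and intervals makes it less likely that a failed test is read as inferiority. It does not change the power or make the sample-size statement correct.

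**Conclusion.** The concern holds. At 80% power, 75 is about 30% (75/252) to 38% (75/198) of the number that XI.2's own inputs require, a gap too large for rounding or choice of formula. If the needles are equally accurate at 80%, the trial has a 33–46% chance of showing non-inferiority, so failure is the more likely outcome.

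This rests on a one-sided alpha of 2.5% to 5%, equal true accuracy of 80%, a margin in percentage points, and 75 evaluable patients per group. The first two are conventional defaults that the available text does not state.

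**What to change.** Replace the sample-size sentence in XI.2 with text along these lines:

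- With 75 patients per group, both accuracies 80% and a margin of 10 percentage points, power is about 33% at one-sided 2.5% or about 45% at one-sided 5% (keep whichever alpha is adopted). The expected two-sided 95% confidence interval for the difference has a half-width of about 13 points.
- If 75 was derived from an assumed Acquire advantage, state the assumed Acquire accuracy with the alpha, sidedness and power used.
- An interval that includes both −10 points and zero will be reported as inconclusive, not as inferiority or equivalence.

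This changes wording in XI.2 only and needs no extra patients. The cost is that the stated justification becomes less favourable. Enlarging the trial to conventional power is a separate decision: it would take 396 (2 × 198) to 504 (2 × 252) patients at 80% power, against the roughly 200 eligible patients estimated in VI.14.
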